Given the dearth of useful and likeable apps ⁵⁴, the need for improving medication adherence in PLWH and the great promise that mHealth holds, we propose to test a smartphone app linked to a smart pill box called CleverCap™ Lite (The Wise App) for PLWH targeting ART adherence and guided by a rigorous and relevant theoretical framework⁵⁵. The feasibility of the Wise App is supported by data demonstrating that use of mobile devices is nearly ubiquitous in the U.S. with persons from underserved groups being more likely to own a smartphone and more likely to use a smartphone (as compared to a computer) to access the Internet. The current trial is significant in representing one of the first principled and systematic efforts to build a mHealth app intervention based on user-centered design work and linked to a smart pill box for improving health outcomes. Our proposed study, based on our empirical findings from our preliminary work ⁵⁶⁻⁶¹, uses rigorous methods and a theory-based approach ⁵⁵ to develop and test a mHealth intervention (Wise App) for improving ART adherence for PLWH.

STUDY DESIGN

The goal of this study is to test the efficacy of The Wise App for improving health outcomes (as measured by improving ART adherence) in PLWH. Our secondary outcomes are: (a) healthcare access (b) technology

acceptance (c) technology use. Table 1 presents and overview of the design, participants and data analysis plan for each aim.

Table 1. Overview of Design, Methods, Participants, and Data Analysis			
Aim	Design/Methods	Participants	Data Analysis
1	Cognitive Walkthrough, and user testing using think-aloud protocol	Cognitive Walkthrough: human-computer interaction experts (N=5); User testing: PLWH (N=30)	Quantitative and qualitative summary of heuristic violations; thematic analysis of think-aloud protocol, quantitative summary of mouse clicks, time, etc.
2	Randomized controlled design	PLWH (N=200; intervention=100, control n=100) for 6 months	Descriptive statistics; Linear regression model
2b	In-depth Interviews	PLWH (N=100; intervention group only)	Qualitative coding of in-depth interviews related to CleverCap device; thematic analysis to examine CleverCap experience and acceptability
3	Descriptive: focus groups	Focus groups: Participants in the intervention arm of the RCT (N~50)	Descriptive, thematic analysis to examine post-intervention perceptions related to The Wise App use, usefulness and impact on overall health

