- **Fitness Tracker (Medium)** – This feature will allow users to track their daily steps. Each user will receive a fitness tracker, which will be synced to the Wise App. A daily step goal will be set for all users and progress will be tracked on the app, allowing users to see the effects of their physical activity.
- **History (Medium)** – Informed by the CleverCap™ Lite dispenser, users will be able to view their medication adherence over time through a graphical representation (Figure 2). The CleverCap™ Lite dispenser uses cellular technology to transmit information on time of pill bottle opening. Users will also be able to view trends of step goals and other app features.
- **Games (Medium)** – Wise App supports two types of gamification: 1) A virtual pet that reacts to a user's medication adherence, and 2) Challenges that can be designed to award/deduct points to users based on select activities completed (Figure 3).

- **Chat (Social Actor)**: This feature will allow study participants to anonymously chat with other users under specific discussion topics. To ensure privacy protection, only study participants will be a part of this chat and all posts will need to be approved by an app administrator prior to being posted.
- **Testimonials of Lived Experiences (Social Actor)** – Videos of PLWH who share their experiences which has the potential to provide social support. Videos will include

topics such as a new diagnosis, living with HIV for 20 years or longer, and disclosing HIV status.

After the Wise App has been built, we will conduct usability testing at the Columbia University School of Nursing.

C.2. Usability Testing.

The goal of usability testing is to improve the design and increase the likelihood of technology acceptance. To achieve this goal we will evaluate the user interface of the Wise App developed at Pattern Health Technologies. We will conduct two types of usability assessments: A) Cognitive Walkthrough and B) End-User Usability Testing.

C.2.1. Cognitive Walkthrough:

[figure not shown]

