Sample: 30 PLWH will be recruited to identify usability concerns within the Wise App. Of the 30 PLWH, 15 will be iPhone users and 15 will be Android users. In usability testing the minimum percentage of problems identified rose from 82% up to 95% when the number of users was increased from 10 to 20.⁶⁶

Procedures: Participants will be provided with a beta version of the Wise App, a Clever Cap, and a fitness tracker. They will be also provided with the same set of user scenarios used for CW by experts. Each participant will be asked to perform tasks which should closely mirror the intended end users of the app. Each participant will be also encouraged to verbalize their thoughts about the tasks they are performing. The process will be audio- and screen-recorded using Morae software™ (Techsmith Corporation, Okemos, MI).⁶⁵ After the usability evaluation, participants will be asked to complete an online survey including a demographic questionnaire and user satisfaction assessment via Qualtrics®. Participants will be compensated \$25.00 for their time.

Data Analysis: The analysis will be based on the Morae recordings of user sessions, transcriptions, and notes. [name] will search for critical incidents which will be characterized by comments, silence, and repetitive actions. [name] will review these incidents in detail using Morae software. The incidents identified and the users' written comments will be summarized. Content analysis, a technique for making replicative and valid inferences from data, will be performed by the research assistant under [name] supervision. The comments will be categorized according to the positive characteristics, negative characteristics, and recommendations made by PLWH. Results from the user satisfaction assessment will be analyzed using SPSS (IBM, Armonk, NY) to calculate the descriptive statistics to complement the findings from the usability assessment in which the PLWH will be using the Wise App. Using the findings from these activities, we will refine the components of the app for use in the RCT (Aim 2).

D. Aim 2: Evaluate the impact of the Wise App on medication adherence in underserved PLWH

D.1. Design Overview.

A randomized controlled trial will be conducted with 200 PLWH over 6 months. Participants will be randomly assigned to the Wise App (intervention) or a control arm.

Details on the differences between the two groups can be found in Table 2.

D.2. Eligibility Criteria for Participants.

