Following the completion of the baseline study instruments, study participants in both arms will be given a CleverCap™ Lite dispenser and trained on how to use it, as well as a fitness tracker that will be synced to Wise App. Study participants in both arms will be trained by study team members on how to use the different features of the Wise App. Those in the intervention group will receive medication reminders while those in the control group will receive reminders about completing their step goal. Participants in both arms will be given a document that includes contact information for the project team, information about compensation, study reminders, and will also receive a telephone call from a research assistant 1 week after enrollment to assist with any technical problems with the app or the CleverCap™ Lite dispenser and biweekly thereafter.

Participants will be texted appointment reminders for study visits via Qualtrics. Hard to reach participants will also be sent scheduling reminders through the Qualtrics system and encrypted e-mails from the study's secure CUMC e-mail address.

Token of appreciation: Participants will be given \$40 at the baseline visit, \$50 + up to an extra \$25 for app challenges completed at the 3 month visit, and \$60 + up to an extra \$25 for app challenges completed at the 6 month visit (up to a total of \$200 for participation) and for providing a blood sample (or recent lab results) for viral load/ CD4 testing and completion of study questionnaires. Participants will also have the option to have the cost of their transportation to and from the study site paid for, through a ridesharing service.

D.8. Operationalization of Outcome Measures.

The primary outcome will be ART adherence, measured by the CleverCap™ dispenser. The CleverCap™ dispenser will automatically record each time a participant opens the dispenser. We will collect adherence data each day from the start to the end of trial (day 1 to 6 months), and it is a count response (number of times taking medication each day). Frequency of app use will be counted each time a participant opens the app.

Table 3. Study Measures

Tool		Measurement Time Points
Demographic Variables and Potential Confounders		
Socio-demographic characteristics	Gender, age, education, income, employment, health insurance, housing	Baseline
Behavioral Data	Use of condoms, tobacco, alcohol, substance use	Baseline, 3 and 6 months

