F.4. Triangulation of Findings. The research team will use the findings from our quantitative data analysis of medication adherence and technology acceptance in Aim 2 to understand use and perceived usefulness of the Wise App. For example, if a participant uses the app component of appointment reminders but does not score well on the Health Care Climate Questionnaire, then further exploration through the focus group sessions will be conducted to determine whether the appointment reminder component is improving health behaviors.

Field notes and transcripts will be analyzed by the researchers using NVivo™ (QSR International, Victoria, Australia) software. Participants' statements will be captured using memoing and then sorted into the following categories of interest: predisposing, enabling and reinforcing. These activities will result in a greater understanding of the use of the Wise App based upon the predisposing, enabling, and reinforcing factors identified in the focus groups. Each focus group recording will be transcribed; transcripts will be analyzed by [name], who is experienced in qualitative analysis and a research assistant. The research team is experienced with these methods ^{91,95-97}.

G. Aim 3b: Assess PLWH perceptions, experience, and satisfaction on the use of the Fitness Tracker that was synced to the HealthStar app through focus group sessions.

G.1. Sample. Post-intervention, we will conduct up to eight focus group sessions with approximately 8-12 participants per group. Focus group participants will be drawn from the control study arm (N~60).

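### As described, the trial tests medication reminders against step-goal reminders within the same app and smart bottle, so the claim of Wise App efficacy needs narrowing

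*Combined protocol and SAP*

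**What the plan says.** The aim is set in Study Design: "The goal of this study is to test the efficacy of The Wise App for improving health outcomes", with improved ART adherence as the measure. The end of the rationale defines the product as "a smartphone app linked to a smart pill box called CleverCap™ Lite (The Wise App) for PLWH targeting ART adherence", so the pill box is part of what is named. D.1 follows this framing: "Participants will be randomly assigned to the Wise App (intervention) or a control arm". The Aim 2 heading speaks of the impact of the Wise App, and D.4 and D.6 also set Wise App against control.

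D.7 describes what each arm receives. Both arms get a CleverCap and a tracker synced to the app, and "Study participants in both arms will be trained by study team members on how to use the different features of the Wise App". The arms then separate on one point: "Those in the intervention group will receive medication reminders while those in the control group will receive reminders about completing their step goal". Table 2 lists the two reminder types under the app and shows the CleverCap for both arms.

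Aim 3b confirms that controls used the app. It asks control-arm participants about "use of the Fitness Tracker that was synced to the HealthStar app", and the rationale says that HealthStar is what the protocol calls the Wise App.

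**The concern.** The wording of the goal and the randomised contrast do not match. A reader of the goal and D.1 would expect the primary result to show whether having the Wise App improves adherence. A reader of D.7 would expect it to show whether medication reminders improve adherence among people who all have the Wise App and the smart bottle.

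These questions can have different answers. If the bottle, the monitoring or other common features help, both arms improve and the contrast does not show it. A null finding could then be reported as failure of the app when only the reminder was tested. A positive finding could be credited to the whole package when the randomised evidence bears on one part of it.

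**Working it through.** **1. Components by arm, as stated**

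| Component | Intervention | Control | Source |
|---|---|---|---|
| Wise App, with training in its features | yes | yes | D.7; Aim 3b for controls |
| CleverCap | yes | yes | D.7, Table 2 |
| Synced fitness tracker | yes | yes | D.7 |
| Medication reminders | yes | no | D.7 |
| Step-goal reminders | unclear | yes | D.7, Table 2 |
| History graph, virtual pet, challenges, chat, videos | not split by arm | not split by arm | C.1 |

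Step-goal reminders are marked unclear for the intervention arm because D.7 mentions them only for controls, while Table 2 may give that arm both types. In the text available to me Table 2 shows two ticks for intervention and one for control, with their alignment lost. That is a limit of the text and not an error in the plan.

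**2. What the primary coefficient estimates**

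D.9 models the log-odds of taking a dose as β0 + β1·t + β2·t·INT plus a person effect. The control slope is β1, the intervention slope is β1 + β2, and β2 is their difference. Write each slope as a sum, assuming additivity on the logit scale:

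- g = change that would occur anyway
- s = effect of everything both arms share (app, bottle, tracker)
- m = effect of medication reminders
- p = effect of step-goal reminders

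Control: β1 = g + s + p.

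Intervention, if it gets medication reminders only: β1 + β2 = g + s + m, so β2 = m − p.

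Intervention, if it gets both types: β1 + β2 = g + s + m + p, so β2 = m.

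The package against no app would be s + m, or s + m + p. The term s is absent from β2 under either reading, so the trial cannot estimate the package effect. If additivity fails, β2 is still a reminder effect, conditional on the shared components being present.

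**3. Reading the result**

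- β2 = 0 implies m = p, or m = 0 if the intervention arm gets both types. It says nothing about s.
- β2 > 0 supports medication reminders, and so the app with them over the app without them. It does not credit the shared components.
- If some features are active in only one arm, β2 also contains their effect. This is why the control configuration has to be stated.

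**4. Whether the plan's power figures can size the point**

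D.4 states 90.7% power for 80% against 86%, and 88.6% for 84% against 89%, with 200 participants, 25% attrition and two-sided alpha 0.05. That leaves 100 × 0.75 = 75 per arm.

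- A two-proportion calculation with 75 per arm gives 16.2% and 14.3%.
- Treating 75 × 180 = 13,500 person-days per arm as independent gives about 100% for both.
- Reaching 90.7% needs about 842 effective observations per arm, or 842/75 = 11.23 per person. The implied intraclass correlation is (180/11.23 − 1)/179 = 0.084. The same steps for 88.6% give 0.075.

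The documents state no such correlation, so the figures cannot be reproduced from the stated inputs. They neither support nor weaken this point, which rests on the component table and the model.

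**The case against.** The best defence is that the design is deliberate and openly described. C.1 lists medication reminders as the sole primary intervention component and everything else as additional. D.1 sends the reader to Table 2 for the difference between arms, and Table 2 shows it. The primary outcome is read from the CleverCap, so a control arm without the bottle could not supply it. All of this stands. It makes the comparison valid, but it does not make that comparison a test of the app linked to the bottle.

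Three stronger readings are tempting, and the documents do not support them.

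- **That the trial can say nothing about the Wise App.** A positive result would be sound evidence for the app with its primary component over the app without it. The claim needs narrowing; the trial is informative.
- **That controls had the adherence graph, the pet, the chat and the videos.** C.1 says that "users will be able to view their medication adherence over time through a graphical representation" without naming an arm, and no section withholds these features from controls. The training sentence and the challenge payments in D.7 are not split by arm either. But no section states that these features were active for controls. Some text suggests a fitness-focused control version: Wise App focus groups draw only on the intervention arm (F.1), the listed control prompts concern the tracker and activity (G.2), and D.8 asks controls about use of HIV or medication apps as a contamination check. The control configuration is therefore unspecified.
- **That the loss can be put in numbers.** D.4's second scenario has controls rising from 80% to 84%, which a reader might take as app benefit lost to the comparison. The scenario is hypothetical, the plan does not attribute the rise to the app, and subtracting control change is what any controlled trial does. Nor do the documents give a rate of leakage through the chat. C.1 says that "only study participants will be a part of this chat and all posts will need to be approved by an app administrator", and a moderated chat could hardly pass on automated, dose-timed reminders.

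**Conclusion.** The concern holds as a mismatch between the stated claim and the randomised contrast. The primary analysis estimates the added effect of medication reminders delivered through the Wise App, over the same app and bottle with step-goal reminders. It does not estimate the effect of the Wise App package against no app.

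The consequence concerns what may be concluded, in both directions, from the primary result. No numerical size can be given, because nothing in the documents separates the shared part from the reminder part. Sample size, outcome and model are not called into question by this point.

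The conclusion assumes that D.7 describes what was delivered and that no unstated feature difference exists between arms. If the intervention arm also gets step-goal reminders, the contrast becomes medication reminders added to an otherwise equal regimen, and the conclusion about the package is unchanged.

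**What to change.** 1. Restate the goal in Study Design, the Aim 2 heading, D.1 and the primary conclusion as the effect of adding medication reminders within the Wise App, compared with the app with step-goal reminders. Bring the arm labels in D.4 and D.6 into line.
2. Add one sentence saying that the trial does not estimate the app package against no app, so a null result is not evidence that the app is ineffective and a positive result supports the reminder component.
3. Reconcile Table 2 with D.7 on whether the intervention arm also gets step-goal reminders, since this decides whether the coefficient is m − p or m.
4. State which app features are active in the control arm.

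The cost is wording, plus a narrower headline claim than efficacy of the Wise App. Allocation, outcome, model and sample size stay as they are.

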3b	Descriptive: focus groups	Focus groups: Participants in the control arm of the RCT (N~60)	Descriptive, thematic analysis to examine post-intervention perceptions related to the Fitness Tracker use, usefulness and impact on overall health
3c	Descriptive: in-depth interview	In-depth interview: Participants in the intervention and control arms of the RCT (N~20)	Descriptive, thematic analysis to examine perceptions related to the recruitment process and research participation to the RCT

C. Aim 1: Build a functional app for HIV self-management linked to a smart pill (Wise App) for PLWH and assess its usability

C.1. Intervention Components.

Medication adherence can be monitored using the CleverCap™ Lite bottle, which emits a cellular signal when it is opened, allowing for near real-time acquisition of data regarding patient pill taking activity. The CleverCap™ Lite adherence monitor (see Compliance Meds Technologies, North Miami Beach, Florida) communicates dosing behavior in real-time by transmission of a patient identifier and date-time stamp over existing cellular networks when the container is opened to take medications.

The primary intervention component will include:

- Medication Reminders – Reminders will be tailored to participants' medication schedule (*Figure 1*). To avoid notification fatigue, a cellular signal is sent to the phone when the servers detect a pill bottle opening, which prevents the launching of the reminder notifications on the phone. The app will launch an in-phone pop-up alert before a scheduled dose time is missed. If the Wise App does not receive notification that the pill bottle has been opened, additional reminders will be launched on the phone after the scheduled dose, asking the patient to taken their medication.

Additional app components are listed below and organized according to Fogg's Functional Triad:

Figure 1. Medication Schedule

[figure not shown]

Figure 2. Mobile App Screen of User History

- **Missions (Tool)** – Missions are intended to help users keep track of activities they enjoy. This feature will display a checklist of tasks participants aim to complete (e.g. go to the gym, text/email a friend, etc.)

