Persons living with HIV/AIDS in this study will be recruited from the HIV clinic at CUMC/NewYork-Presbyterian Hospital and AIDS Service Center.

There is no more than a **minimal risk** associated with any of the proposed study activities. The study activities meet the general definition found in Subpart A (46.102) that the probability and magnitude of harm or discomfort anticipated in the research are not greater in and of themselves than those ordinarily encountered in daily life or during the performance of routine physical or psychological examinations or tests.

Following IRB approval, all study participants will provide informed consent prior to their participation in this study.

b. Sources of Materials

Subjective data (e.g., health status, quality of life) and system use will be obtained from subjects for the specific research purposes of this study.

b.1. Access to Individually Identifiable Private Information about Human Subjects

Access to individually identified private information about human subjects will be limited to research team members who collect and manage the data, the project coordinator, and the PI. De-identified data will be accessible by all members of the research team involved in the data analysis.

c. Potential Risks

The risks of participating in this study are few. Some of the questions on the questionnaires may make the subject uncomfortable or upset, but the subject is free to decline to answer any questions. Participation in research can involve loss of privacy. Information about the subject will be handled as confidentially as possible. All study data will be maintained in a completely secure and HIPAA compliant environment. All CUMC servers have HIPAA compliant security. All signed consent forms and payment receipts used in this study will be kept in locked files so only the investigators will have access to the files.

Adequacy of Protection against Risks

a. Recruitment and Informed Consent/Accent

Recruitment for participation in the study will occur following approval by the CUMC IRB. The PI will determine eligibility for inclusion, explain the purpose of the study, answer any questions, and obtain written consent from the participants.

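### A bottle that stops transmitting is more likely to be noticed in the intervention arm than in controls, and neither the support calls nor the analysis allows for that

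*Combined protocol and SAP*

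**What the plan says.** **How reminders work (C.1, Medication Reminders).** When an opening is detected, "a cellular signal is sent to the phone when the servers detect a pill bottle opening", and this holds back the reminder. Otherwise: "If the Wise App does not receive notification that the pill bottle has been opened, additional reminders will be launched on the phone". The trigger is the absence of a notification, not a confirmed missed dose.

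**Who gets them (D.7 and Table 2).** "Those in the intervention group will receive medication reminders while those in the control group will receive reminders about completing their step goal". Both arms use the dispenser.

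**Technical support (D.7).** Participants in both arms "will also receive a telephone call from a research assistant 1 week after enrollment to assist with any technical problems with the app". The sentence runs on, so the full scope is "technical problems with the app or the CleverCap™ Lite dispenser and biweekly thereafter". The calls therefore cover the bottle as well as the app, and they recur in both arms. They are described as assistance. No test opening, review of the server log or alert for prolonged silence is mentioned.

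**Other ways a fault could surface.** D.7 also says: "Study participants in both arms will be trained by study team members on how to use the different features of the Wise App". C.1 lists a History graph fed by the dispenser and a virtual pet that responds to adherence, and limits neither to one arm. The Aim 2b interviews about the device, at 3 months, are for the intervention arm only. D.8 collects the CASE index, CD4 and viral load in both arms at baseline, 3 and 6 months to validate the dispenser data.

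**Outcome (D.8 and D.9).** The primary outcome is the daily count of bottle openings, modelled as binomial, from day 1 to day 180. Missing adherence data are mentioned only for a secondary as-treated analysis, where they are ignored.

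**The concern.** The point is about bottles that are still used every day but no longer reach the server. D.8 already recognises a different problem, namely that controls may stop using the device. It does not mention loss of transmission during continued use.

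The reminder system doubles as a fault detector, and only one arm has it. If faults occur equally often in both arms but are found and repaired sooner in the intervention arm, more genuine openings are lost among controls. Recorded control adherence then falls without any change in pill-taking, and the primary comparison moves towards the intervention. D.9 carries the arm contrast only in the time-by-intervention term, so control losses that build up during follow-up would enter the tested parameter.

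**Working it through.** **The plan's own figures.** The plan gives no fault rate, detection time or signal-loss figure, so there is nothing on this point to reproduce. The nearest figure is the 90.7% power in D.4 for 80% against 86%. With 25% attrition, 100 × 0.75 = 75 remain per arm. Taking persons as units, two-sided 0.05, power is 16.2%. Taking 75 × 180 = 13,500 person-days per arm as independent, it is about 100%. The stated value lies between and implies a between-person SD of about 0.112, which D.4 does not give. That is a missing input; nothing below depends on it.

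**Which faults matter.** C.1 describes two links.

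- *Bottle to server.* If this fails, the opening never reaches the outcome data. In the intervention arm it also triggers a reminder after the dose was taken.
- *Server to phone.* If this fails, the intervention participant gets a false reminder, but the opening is already on the server and the outcome is intact.

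Only the first link can bias the primary result.

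**Detection routes for a bottle-to-server fault.**

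| Route | Intervention | Control |
|---|---|---|
| Reminder pushed after a dose already taken | Yes | No |
| Support calls, week 1 then biweekly | Yes, if the participant raises it | Yes, if the participant raises it |
| History graph, virtual pet | Must be looked at and interpreted | Same, if controls have them; not stated |
| Aim 2b device interview, 3 months | Yes, optional | No |
| CASE and viral load against bottle data, 3 and 6 months | Possible; no action rule | Possible; no action rule |

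The first and fourth rows differ by arm, both in the same direction.

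**Illustrative size.** Inputs:

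- Follow-up of 180 days (D.9).
- True adherence of 80% in both arms (the D.4 baseline value).
- Share of bottles failing once: 5%, 10% or 20% (assumed).
- Fault duration in the intervention arm: 7 days (assumed; about half of a two-week gap between calls).
- Fault duration in controls: 45 days (assumed; about half of the three months between visits) or 30 days (assumed).
- All openings during a fault are lost and scored as zero (assumed).

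Spurious difference = failing share × (control days − intervention days) / 180 × 0.80.

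| Failing share | 45 vs 7 days: share × 38/180 × 0.80 | 30 vs 7 days: share × 23/180 × 0.80 |
|---|---|---|
| 5% | 0.8 points | 0.5 points |
| 10% | 1.7 points | 1.0 points |
| 20% | 3.4 points | 2.0 points |

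These are averages over 180 days. D.4's differences of 5 and 6 points are at the end of the trial, and D.9 tests a difference in change on the logit scale. Converting one to the other needs an assumption about when faults occur, so the figures should not be read as a fraction of the planned effect.

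**The case against.** The strongest reply is that the plan already has working safeguards. Both arms receive calls expressly covering the dispenser, about 13 in 26 weeks if biweekly means every two weeks (weeks 1, 3, …, 25). Both arms are trained on the app, and the History graph and virtual pet could reveal lost openings to controls. CASE and viral load give an independent check. D.9 does not actually say that a day without signal is scored as zero, and the documents do not say whether a bottle stores openings and sends them later. Every number in the size calculation other than 180 days and 80% is assumed.

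Much of this stands. A reader might infer that a fault stays hidden in controls. The documents do not support that: they support only that it is less likely to be noticed, because controls would have to look at a screen and interpret it, while intervention participants receive a push. A reader might also assume that control faults are never found, giving larger distortions, but recurring calls that cover the dispenser make that hard to defend.

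A reader might further infer that the risk section contradicts the reminder rule, since it states "The risks of participating in this study are few" and does not list prompts for doses already taken. A short list that omits an item is not a contradiction, and the consent pages are not in the available text, so disclosure there cannot be judged.

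What the reply does not remove is that the calls contain no signal check, the extra cues run one way, CASE and viral load come only at 3 and 6 months with no rule for acting on discordance, and the count model has no category for a silent bottle.

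**Conclusion.** The concern holds in a limited form. The mechanism follows from C.1, D.7 and D.9: a bottle-to-server fault is likelier to be noticed in the intervention arm, and slower detection in controls would bias the primary comparison towards the intervention. The direction is clear provided that faults occur equally in both arms and that silent days are counted as not opened, which is the default reading of D.9 but not an explicit rule.

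The size is not known. About 0.5 to 3.4 points follows from assumed fault shares and durations and shows only that the effect need not be negligible. Confidence in the size is low. The change should still be made, because it is cheap and protects the primary outcome.

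**What to change.** **D.7.** At the week-1 call and each biweekly call, in both arms, have the caller confirm on the server that the bottle is transmitting. Review the recent log first; only if it is silent, ask for one test opening and see whether it arrives. Log the result, replace a failed bottle, and remove test openings from the outcome.

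**D.9.** State that days of confirmed device failure, from the last received transmission to replacement, are missing in both arms. Add a sensitivity analysis scoring them as zero. Report the number and duration of failures by arm.

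**C.1 and Table 2.** State whether controls have the History graph and virtual pet.

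**Risk section.** Record prompts for doses already taken at the same calls, and check that the risk text covers them.

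**Cost.** About a minute per call: at most 200 × 13 = 2,600 checks, or roughly 43 hours over the trial, plus some replacement bottles. A test opening is a small handling cue; applying the same rule in both arms, and only when the log is silent, limits it. Some true non-adherent days just before a failure may be set to missing; the sensitivity analysis shows how much that matters.
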